Chelsea and Westminster Hospital
[name]

Co-investigator **[name]**
Respiratory Nurse Specialist
Chelsea and Westminster Hospital
[name]

3 Study synopsis

Study number:	10.0086
Study drug:	Metformin
Title of the study:	A randomised, double-blind, placebo-controlled trial of metformin in chronic obstructive pulmonary disease exacerbations: a pilot study
Chief Investigator:	[name] Professor of Clinical Pharmacology Division of Biomedical Sciences St George's, University of London [name]
Study centres:	
 • St George's Healthcare NHS Trust • Chelsea and Westminster Hospital NHS Foundation Trust • Conquest Hospital, East Sussex Healthcare NHS Trust • Freeman Hospital, Newcastle upon Tyne NHS Foundation Trust • Kings Mill Hospital, Sherwood Forests NHS Foundation Trust • University Hospital of North Tees, North Tees & Hartlepool NHS Foundation Trust • Blackpool Victoria Hospital, Blackpool, Fylde and Wyre Hospitals NHS Foundation Trust • Royal Preston Hospital, Lancashire Teaching Hospitals NHS Foundation Trust • Royal Lancaster Infirmary, University Hospitals of Morecambe Bay
Study period:	01/07/2010 – 01/07/2014
Clinical phase:	03/01/2011 – 31/03/2014
Primary Objective:	To determine whether, in patients hospitalised for COPD exacerbations and receiving conventional treatment, the addition of metformin, as compared with placebo, ameliorates hyperglycaemia.
Secondary Objective:	To determine whether, in patients hospitalised for COPD exacerbations and receiving conventional treatment, the addition of metformin, as compared with placebo, produces effects on clinical outcome, and measures of inflammation, steroid sensitivity, and airflow obstruction, which merit further study.
Study population:	Patients hospitalised for COPD exacerbations and expected to stay in the hospital for ≥ 48 hours. The target sample size is 69 patients.
Methodology:	Randomised, double-blind, placebo-controlled trial. Patients will be randomised in a 2:1 ratio to metformin or matched placebo. Treatment will be commenced at randomisation and continued until follow-up at day 28–35.

Main Inclusion and Exclusion criteria:*Inclusion criteria:*

1. Diagnosis of COPD
2. Hospitalisation for exacerbation of COPD
3. Age ≥ 35 years
4. Expected to remain in hospital for ≥ 48 hours.

Exclusion criteria:

1. Prior diagnosis of diabetes mellitus requiring insulin or oral hypoglycaemic therapy
2. Hypersensitivity to metformin hydrochloride or to any of the excipients
3. Renal impairment
4. Severe sepsis
5. Metabolic acidosis
6. Decompensated type 2 respiratory failure
7. Severe congestive cardiac failure
8. Acute coronary syndrome
9. Hepatic insufficiency
10. Excessive alcohol consumption
11. Malnourished or at high risk for malnutrition
12. Moribund or not for active treatment
13. Admitted to critical care unit
14. Unable to give informed consent
15. Pregnancy or lactation

Study drugs, Dose and Mode of Administration

Metformin hydrochloride 1000 mg twice daily or matched placebo, administered orally.

Duration of Treatment

28–35 days

Criteria for evaluation

Primary endpoint:

- Mean capillary glucose concentration during hospitalisation period.

Secondary endpoints:

- Clinical efficacy: COPD Assessment Test score, Exacerbation of Chronic Pulmonary Disease Tool (EXACT) score, time to medical fitness for discharge, time to actual discharge, rates of recurrent exacerbation, readmission (any cause), or death (all cause).
- Glycaemic control: mean daily insulin use during hospitalisation period, mean haemoglobin A1c and serum fructosamine concentrations at follow-up
- Inflammation and infection: mean C-reactive protein and serum cytokine concentration at discharge and follow-up (absolute values and change from baseline)
- Other metabolic effects: mean body mass index at follow-up, mean waist circumference at follow-up
- Airflow limitation: FEV₁ at 4 weeks
-

4 Introduction

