6.2 Study population

The sample size was originally set at 46 patients, randomised equally to metformin or placebo. From Substantial Amendment 4 approval, this is increased to 69 patients, randomised to metformin or placebo in a 2:1 ratio. The patients will be drawn from the population of patients admitted to the study sites with an exacerbation of COPD, and who are able to enter the study within 48 hours of admission.

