9.6 Summary flow chart of study assessments

Day	IMP administration	Assessments
1	One capsule	Capillary glucose concentration (thereafter repeated before and 2 hours after each mealtime, and at approximately 22:00) COPD Assessment Test (CAT) Exacerbations of Chronic Pulmonary Disease Tool (EXACT) Malnutrition Universal Screening Tool (MUST) Renal profile, liver profile, CRP, lactate, random glucose, HbA1c Serum sample saved
2	One capsule twice daily	Exacerbations of Chronic Pulmonary Disease Tool (EXACT) Capillary glucose (as above) CRP Food chart if admission MUST score 1 (medium risk)
3	Two capsules morning, one capsule evening	Exacerbations of Chronic Pulmonary Disease Tool (EXACT) Capillary glucose (as above) CRP measured daily to day 7 Food chart if admission MUST score 1 (medium risk)
Day 4 until discharge	Two capsules twice daily	Exacerbations of Chronic Pulmonary Disease Tool (EXACT) Capillary glucose (as above) CRP measured daily to day 7 Safety parameters (renal function, liver enzymes, plasma lactate, venous glucose) measured at least every 72 hours until day 7 (more often if deemed necessary by study team or clinical team), then at a frequency appropriate for the clinical condition of the patient (no less often than once-weekly)
Day of discharge	Two capsules twice daily	Capillary glucose (as above, until time of discharge) Exacerbations of Chronic Pulmonary Disease Tool (EXACT) COPD Assessment Test Spirometry CRP Serum sample saved
Day of discharge until follow-up	Two capsules twice daily	Exacerbations of Chronic Pulmonary Disease Tool (EXACT)
Follow-up (day 28–35)	Two capsules in the morning	Structured interview and pill count COPD Assessment Test (CAT) Weight, height and waist circumference Spirometry Venous glucose, HbA1c, lactate, CRP Serum sample saved
12 weeks	None	Vital status (electronic patient record) Hospital admissions (self-reported and electronic patient record) COPD Assessment Test (returned by post) Antibiotic and steroid courses (self-reported) Diagnosis and/or treatment for diabetes (self-reported)

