14.2.2 Secondary endpoints

Unless otherwise specified, the endpoints described below related to a comparison of data between the active treatment and placebo groups.

Clinical efficacy:

- COPD Assessment Test score at 4 weeks and, where available, at 12 weeks—defined as the sum of the points marked on the patient-completed COPD Assessment Test, as published; comparisons of mean score at follow-up and proportion of patients with improvement ≥ 5 points
- Exacerbation of Chronic Pulmonary Disease Tool (EXACT) scores—mean scores at days 5, 10 and 28
- time to medical fitness for discharge—defined as the number of days between study enrolment and the day on which the patient is documented by the clinical care team to be medically fit for hospital discharge, if this is different to the date of actual discharge
- time to actual discharge—defined as the number of days between study enrolment and the day on which the patient is discharged from the hospital
- rates of recurrent exacerbation, readmission, or death—defined, respectively as the number of days between study enrolment and the day on which the patient is prescribed a systemic antibiotic or steroid (for an exacerbation of COPD), is readmitted to hospital (for any reason except planned elective treatment or investigation), or dies (from any cause)

Glycaemic control:

- mean daily insulin use during hospitalisation period—defined as total number of units of insulin administered (of any formulation), divided by the duration of hospitalisation (in days)
- mean HbA1c and serum fructosamine concentration at follow-up, and change from baseline

Inflammation and infection:

- mean C-reactive protein concentration at discharge and follow-up (absolute values and change from baseline)
- a relevant panel of markers of inflammation and oxidative stress, measured on serum samples collected at study entry, discharge and follow-up (absolute values and change from baseline)

Other metabolic effects:

- mean body mass index at follow-up
- mean waist circumference at follow-up

Airflow limitation

- FEV₁ at 4 weeks—mean values at follow-up and mean change from discharge

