14.4.3 Secondary endpoint analysis

This study has not been powered for its secondary endpoints. The secondary analyses are for the purpose of hypothesis generation, rather than to provide firm conclusions. This study will inform the design of a future larger trial.

Means will be compared using the t-test (for normally-distributed continuous data), Mann-Whitney test (for non-normally-distributed continuous data), or Chi-square or Fisher's exact test as appropriate (for categorical data). Time-to-event data will be analysed and presented using Kaplan-Meier curves, the log rank test, and Cox proportional hazards regression.

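### CRP and serum markers are compared as absolute values and as raw change from Day 1, both without adjustment for the Day 1 value, so neither uses it efficiently and the change score may lose much of its power.

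*Protocol*

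**What the plan says.** Protocol section 3 (synopsis, criteria for evaluation) gives the inflammation endpoints as "mean C-reactive protein and serum cytokine concentration at discharge and follow-up (absolute values and change from baseline". Section 14.2.2 gives CRP as "mean C-reactive protein concentration at discharge and follow-up (absolute values and change from baseline" and adds a panel of inflammation and oxidative-stress markers "measured on serum samples collected at study entry, discharge and follow-up (absolute values and change from baseline".

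The baseline is the Day 1 sample. The flow chart in section 9.6 lists for that day "Renal profile, liver profile, CRP, lactate, random glucose, HbA1c Serum sample saved". Section 6.2 draws on patients "who are able to enter the study within 48 hours of admission", so Day 1 falls early in the acute admission. Follow-up is at day 28–35.

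Section 14.4.3 sets the tests for all secondary endpoints: "Means will be compared using the t-test (for normally-distributed continuous data), Mann-Whitney test (for non-normally-distributed continuous data". It names no baseline covariate and no transformation. Section 14.4.5 plans no sensitivity or other analyses. No section says whether the absolute value or the change is the main form.

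**The concern.** A change score subtracts the whole Day 1 value. If Day 1 values vary much more between patients than later values do, the change is close to minus the Day 1 value, which treatment cannot have affected. The comparison then carries noise that has nothing to do with the drug. A rank test does not remove this, because the ranks of the change largely follow the ranks of the Day 1 value. The absolute-value comparison avoids that noise but discards what the Day 1 value could explain.

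Inflammation is a named secondary objective. Section 5.2 says the secondary data will help to choose endpoints and sample sizes for a larger trial. Two equally ranked and possibly conflicting results for each marker serve that purpose poorly.

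**Working it through.** **Inputs.** From the protocol: 69 patients at 2:1, taken as 46:23 (section 6.2); two-sided 5% level (section 14.4.2). The protocol states no CRP or cytokine level, spread, correlation or power, so there is no plan figure to reproduce. Assumed: k = Day 1 SD / later SD, from 1 to 5; r = correlation of Day 1 and later values, from 0 to 0.7.

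**Closed form, relative to the variance of the later value.**
- Absolute value: 1
- Change: 1 + k² − 2rk
- Later value adjusted for Day 1 value: 1 − r²

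The change minus the adjusted variance is (k − r)², which is never negative. Apart from one degree of freedom, adjustment is therefore never worse than either planned form. The change beats the absolute value only if r > k/2, which is impossible once k is 2 or more.

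**Share of the change explained by the Day 1 value:** (k − r)² / (1 + k² − 2rk).
- k = 2, r = 0.5: 2.25 / 3.0 = 0.75
- k = 5, r = 0.7: 18.49 / 19.0 = 0.97
- k = 1: from 0.50 (r = 0) down to 0.15 (r = 0.7)

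**Power at 46:23** (noncentral t), with the true effect set at 0.726 later-SD so that the absolute value has 80%:

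| k | r | Change variance | Change | Adjusted |
|---|---|---|---|---|
| 1 | 0.2 | 1.6 | 60% | 82% |
| 1 | 0.5 | 1.0 | 80% | 90% |
| 1 | 0.7 | 0.6 | 95% | 97.5% |
| 2 | 0.3 | 3.8 | 30% | 84% |
| 3 | 0.3 | 8.2 | 16% | 84% |
| 5 | 0.3 | 23.0 | 9% | 84% |

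**Chance imbalance.** The standard error of a Day 1 difference between arms is √(1/46 + 1/23) = 0.255 Day 1 SD. At k = 3 that is 0.77 later-SD, about the size of the effect sought (0.73).

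**Simulation on skewed data.** Assumed: lognormal CRP, Day 1 median 20–40 mg/L (log SD 1.2), later median 6–12 mg/L (log SD 1.0), log-scale correlation 0.2–0.7, true halving on metformin. A lognormal SD is median × exp(s²/2) × √(exp(s²) − 1), which is 3.69 × median at s = 1.2 and 2.16 × median at s = 1.0. So k is about 2.8 for 20 falling to 12, 5.7 for 20 to 6 or 40 to 12, and 11.4 for 40 to 6. Simulated power:
- change by Mann-Whitney: about 8–14% in most pairings (single runs as low as 7%), and 21–38% for 20 falling to 12
- change by t-test: about 3–11%
- absolute value by Mann-Whitney: about 73–75%
- log later value adjusted for log Day 1 value: about 77–97%

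The two planned Mann-Whitney analyses disagreed on significance in roughly 60–76% of simulated trials. With no true effect, rejection stayed near 5% for every method.

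**Where the loss shrinks.** With log SD 1.0 at both times and medians of 12 and 10, change by Mann-Whitney has 38–77% power for r from 0.3 to 0.8. With log SD 0.6 at both times, r = 0.8 and a 30% reduction, change (74–86%) beats the absolute value (about 60%).

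**The case against.** The strongest reply is that the plan does not rest on change scores. It also compares absolute values, which carry no Day 1 noise and have about 73–75% power in the simulated setting. A reader might infer that the plan as a whole will conceal a real anti-inflammatory effect, or that the change score will look null whenever the drug works. The documents do not support either. One of two planned comparisons is weak in part of the plausible range, and in another part it does well.

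Four further points stand:
- The loss is of power. Allocation is randomised, so the change comparison is not biased.
- A reader might take Day 1 as the peak of the exacerbation. The protocol says only that entry is within 48 hours of admission. The spread of CRP on that day is an assumption.
- The CRP pattern need not carry over to every marker. Section 4.5.3 describes antioxidant capacity as low during exacerbations and recovering later, so some oxidative-stress markers may behave differently.
- Section 14.4.3 says "The secondary analyses are for the purpose of hypothesis generation, rather than to provide firm conclusions". Because both values are collected, an adjusted SD for a later trial can be computed whatever test is reported.

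It can also be said that covariates and transformations belong in a separate statistical analysis plan, which is not at hand. That carries less weight here: the protocol itself fixes the two endpoint forms and the unadjusted tests. For skewed CRP the t-test figures matter little, since section 14.4.3 would send such data to Mann-Whitney.

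**Conclusion.** The point holds as a matter of efficiency. Sections 14.2.2 and 14.4.3 set absolute value and raw change side by side, compare both without adjustment, and name neither as the main form. If the Day 1 SD is 2 to 5 times the later SD, the Day 1 value accounts for about 75–97% of the variance of the change. An effect with 80% power on the absolute value then has about 30% down to 9% on the change at r = 0.3. In the skewed CRP scenario the figures are about 8–38% for change and 73–75% for the absolute value, both by Mann-Whitney, against 77–97% after adjustment on the log scale.

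These sizes rest on assumed spreads and correlations. With similar spread at both times the change score loses little or nothing, and at high correlation it can beat the absolute value. Adjustment remains the best of the three throughout. For unpowered, hypothesis-generating endpoints this is an improvement of low to moderate priority.

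**What to change.** In sections 14.2.2 and 14.4.3, with the synopsis aligned, name one between-arm analysis per marker and time point: a regression of the later value on treatment arm and Day 1 value. Use the log scale for CRP and for any serum marker that is right-skewed, and another suitable scale otherwise. Report the effect with a 95% confidence interval, as a ratio of geometric means where logged. Keep absolute values and changes as descriptive summaries by arm.

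The cost is wording only, since the Day 1, discharge and follow-up samples are already scheduled. A convention for values below the assay limit must be fixed in advance, and logged effects read as ratios instead of differences in mg/L.

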7.1 Inclusion criteria

(1) Diagnosis of COPD based on at least one of the following criteria:

- Previously recorded airflow obstruction on spirometry (FEV1 <80% predicted, FEV1:FVC <70% predicted), without evidence of complete reversibility
- Previous diagnosis of COPD by a respiratory physician
- Exertional breathlessness, chronic cough, or regular sputum production, in a patient who has ≥10 pack-years smoking history

(2) Hospitalisation for exacerbation of COPD, defined by the presence of at least two of the following major features, or one major symptom and one minor feature.

Major features:

- Increased breathlessness
- Increased sputum volume
- Increased sputum purulence

Minor features:

- upper respiratory infection within the past 5 days
- fever without other cause
- increased wheezing or cough
- increase in respiratory rate or heart rate by 20% as compared with baseline

(3) Age ≥35 years

(4) Expected to remain in hospital for ≥48 hours.

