14.4 Statistical analysis plan

14.4.1 Summary of baseline data and flow of patients

The report will detail the number of eligible patients for the trial, the number consenting and the number randomised. A breakdown will be presented for each group of the numbers of participants assigned, receiving the intended treatment, completing the study protocol, and analysed for the primary outcome. This information will be displayed as a flow diagram.

The following data will be used to describe baseline comparability of study groups:

- Age (continuous)—mean and standard deviation

- Sex (categorical)—proportions
- COPD Assessment Test score (interval scale)—mean and standard deviation
- Exacerbation of Chronic Pulmonary Disease Tool score (interval scale)—mean and standard deviation
- Forced expiratory volume in 1 second (continuous)—mean and standard deviation
- Presence of radiographic consolidation (categorical, defined by the presence or absence of consolidation or airspace shadowing on a chest X-ray, as reported by a radiology specialist as part of routine clinical practice)—proportions
- Venous blood glucose concentration (continuous)—mean and standard deviation
- Haemoglobin A1c (continuous)—mean and standard deviation
- C-reactive protein concentration (continuous)—mean and standard deviation

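### Follow-up FEV1 is compared without adjusting for age, sex and height, all of which are recorded; if it is analysed in litres, some precision is given up

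*Protocol*

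**What the plan says.** The synopsis gives the airflow endpoint as "Airflow limitation: FEV₁ at 4 weeks". Section 14.2.2 defines it in full as "FEV₁ at 4 weeks—mean values at follow-up and mean change from discharge", so two comparisons are planned. Neither place states whether FEV1 is in litres or as a percentage of the predicted value.

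For secondary endpoints, section 14.4.3 says "Means will be compared using the t-test (for normally-distributed continuous data"), with a Mann-Whitney test where data are not normal. It names no covariates for means. Section 14.4.5 plans no sensitivity or other analyses.

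The protocol collects the three personal characteristics in question:

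- Section 14.4.1 lists "Age (continuous)—mean and standard deviation" and "Sex (categorical)—proportions" as baseline data.
- Section 9.6 schedules "Weight, height and waist circumference" at the day 28–35 visit, the same visit as the follow-up spirometry.

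Section 14.4.1 also lists "Forced expiratory volume in 1 second (continuous)—mean and standard deviation" as a baseline variable, but section 9.6 schedules spirometry only on the day of discharge and at follow-up. Section 7.1 expresses FEV1 relative to prediction: "Previously recorded airflow obstruction on spirometry (FEV1 <80% predicted, FEV1:FVC <70% predicted").

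**The concern.** Patients differ in FEV1 partly because of sex, age and body size. The protocol recognises this when it uses percent predicted in section 7.1. In a comparison of means in litres, that variation stays in the error term. Treatment over four weeks cannot alter age, sex or adult height, so all three can be used as covariates safely.

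A pre-treatment FEV1 would normally do this job better, but it cannot be relied on here. The schedule contains none, and earlier recorded spirometry is only one of three alternative routes to the COPD diagnosis in section 7.1.

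Airflow obstruction is named in the secondary objectives (section 5.2). The same section says that the secondary data will guide endpoint choice and sample size for a larger trial. An interval wider than necessary makes the data less useful for that purpose.

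**Working it through.** **What the plan calculates.** It gives no standard deviation, effect size or power for FEV1. Its stated totals of 44 (1:1) and 48 (2:1) in section 14.3.1 concern glucose. They reproduce with the usual two-mean formula (22 + 22 and 32 + 16) but do not bear on FEV1.

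**Inputs.** The target is 69 patients at 2:1 (section 6.2), about 46 and 23. Two quantities are not in the documents and are assumed over a range: R², the share of FEV1 variance explained by age, sex and height, and ρ, the within-patient correlation between discharge and follow-up FEV1.

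**1. Unadjusted follow-up mean.**
SE = SD × √(1/46 + 1/23) = 0.255 SD.

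**2. Adjusted for three covariates.**
SE = 0.255 SD × √[(1 − R²) × 67/64], where 67 = 69 − 2 and 64 = 69 − 2 − 3 allow for the lost degrees of freedom.

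| Assumed R² | SE (in SD) | Reduction |
|---|---|---|
| 0.1 | 0.248 | 3% |
| 0.2 | 0.234 | 8% |
| 0.3 | 0.219 | 14% |
| 0.4 | 0.202 | 21% |
| 0.5 | 0.185 | 28% |

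Break-even is where (1 − R²) × 67/64 = 1, so R² = 1 − 64/67 = 0.045. In variance terms, R² = 0.2 gives 0.8 × 67/64 = 0.8375, worth about 19% more patients (1/0.8375 = 1.19).

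**3. The planned change from discharge.**
With equal variances at both visits, SE = 0.255 SD × √[2(1 − ρ)].

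| Assumed ρ | SE (in SD) | Reduction |
|---|---|---|
| 0.5 | 0.255 | 0% |
| 0.7 | 0.198 | 23% |
| 0.8 | 0.161 | 37% |
| 0.9 | 0.114 | 55% |

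Ignoring the lost degrees of freedom, the change score has the smaller SE once 2(1 − ρ) < 1 − R², that is ρ > (1 + R²)/2. This is 0.55 to 0.75 for R² of 0.1 to 0.5.

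**4. What each comparison measures.** Day 4 is the first day at target dose (section 9.5). Section 6.4 reports median stays of 9 days (interquartile range 5–17) and 8 days (4–16). Discharge FEV1 will therefore usually be measured on treatment, and subtracting it removes any effect gained in hospital. Time to discharge is itself a secondary endpoint, so the starting point can also differ between arms. Only the follow-up mean compares the randomised groups on the full effect.

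**The case against.** The strongest reply is that the plan already has a more precise comparison. Age, sex and height are practically constant between discharge and follow-up, so they largely cancel in the change score, and step 3 shows that it can have a smaller SE than the adjusted follow-up mean. That stands. A reader who saw only the synopsis might infer that the airflow comparison as a whole is needlessly imprecise; section 14.2.2 does not support that. But the change score answers a narrower question and cannot replace the follow-up mean.

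Second, the unit is not stated. A reader might infer that FEV1 is fixed as an unstandardised value; the text does not say so. If percent predicted was intended, the three characteristics are already accounted for and only the missing unit needs attention.

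Third, an unadjusted t-test on randomised groups is valid, and section 14.4.3 calls these analyses unpowered and hypothesis-generating. Both points stand. A reader might also infer that a chance imbalance in sex could pass for a drug effect. The interval already allows for such imbalance. With half the patients men (assumed), one standard deviation of the difference in the proportion of men is √[0.25 × (1/46 + 1/23)] = 0.128. Even if sex alone carried all of R², that imbalance would shift the estimate by √R² × SE against a half-width of 1.996 × SE: 22% of the half-width at R² = 0.2 and 35% at 0.5.

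Finally, it might be argued that covariates belong in a separate analysis plan. Often they do, but here the protocol itself prescribes the unadjusted test and says that no other analyses are planned.

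**Conclusion.** The point holds as a modest gain in efficiency for one of the two FEV1 comparisons, and only if FEV1 is analysed in litres. The unadjusted comparison of follow-up means is valid; it is simply less precise than one using data that the trial already collects. The gain in SE is about 3% at R² = 0.1 and 8% to 28% at R² of 0.2 to 0.5, with a loss only below about 4.5%.

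These figures rest on assumed R² and on 46 and 23 patients with follow-up spirometry. Section 14.5 says that the final ratio cannot be predicted exactly, and deaths or missed visits will lower the numbers. The documents do not support a claim that age, sex and height determine most of a patient's FEV1; disease severity matters too, and no R² is given. Nothing here is a bias, and the endpoint is exploratory, so the weight is low.

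**What to change.** - In section 14.2.2, state the FEV1 unit.
- In section 14.4.3, analyse follow-up FEV1 in litres with a linear model containing arm, age, sex and height, and report the adjusted difference with its 95% confidence interval. Alternatively, compare FEV1 % predicted.
- Keep the raw means and the change from discharge as description.

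The cost is a change of wording and three degrees of freedom. No new data are needed: age and sex are baseline items, and height is measured at the same visit as the follow-up spirometry.
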